# 2.10 Sample Size

- This study is a two-stage trial with one planned interim analysis for futility
- Based on the prior 30-month time period (as of May 2022), 572 out of 1071 patients (53.4%) presenting to the ED and meeting the inclusion criteria did not require a 2nd parenteral pain medication during the ED encounter. Thus, we estimate a baseline response rate of 55%.
- Prior work by Nobel et al.¹and Aydin et al.² suggests that no patient will require a second dose of any pain medication after ESPB, but we estimate a conservative response rate of 75% for treatment with ESPB.
- Using Simon's optimal two-stage design with these parameters and  $\alpha$  = 0.05,  $\beta$  = 0.10, we estimate that 18 subjects will be required at the interim analysis and 54 subjects will be required to complete this study.
- Using a Bayesian two-stage design, where interim analysis is planned at one-third total enrollment and a stopping rule if there is only a 10% probability of ESPB demonstrating a 75% response rate, we estimate that 45 total subjects (15 at interim analysis) will be required to achieve a 1.4% chance of stopping early and 95.2% chance of rejecting the null hypothesis.
- This study will aim to achieve a total enrollment of 60 subjects who receive ESPB to account for losses to follow up and withdrawals from the study. Up to 180 (3:1 ratio) historical controls will also be included in the study thus the total enrollment including both treatment and control patients is 240.

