#### 3.6 Outcomes

#### 3.6.1 Primary Outcome and rationale

The primary outcome will be the proportion of patients receiving a second parenteral pain medication in the ED after a single-shot ESPB is performed by a study investigator. We have reviewed historical data that suggests that the rate of response (percentage of patients that do not require a second parenteral pain medication) in patients with urolithiasis, and who receive a parenteral medication as the first analgesic in the ED (approximately 70% of all kidney stone patients), ranges from 47 to 57% for the years 2020 – 2022. The average response rate is 53.4% during this period which is in line with historical trends prior to the Covid-19 pandemic.

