# 4.4 Selection of external control patients

External control patients will be selected from a population of patients meeting the following criteria: 1) adult ED patient with the diagnosis of uncomplicated kidney stones; 2) received at least one dose of parenteral medication while in the ED; 3) presentation to the ED between 7/1/2021 and the study start date. From this population, propensity score matched control patients will be selected at a ratio of 3 controls to 1 ESPB patient. External control population patients are not active patients in this study and analysis of their data will be secondary use of data collected during routine care. To provide valid comparison between control patients and ESPB patients, we will compare pain scores obtained by the treatment team (bedside nurse). For all other primary and secondary outcomes, data collection utilizes EHR query that does not require prospective data collection. Please see the data collection section of this protocol for further details.

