# **5 STUDY PROCEDURES**

# 5.1 Study Design and Workflow

This study is designed to be a pragmatic, single treatment arm two-stage trial that investigates the efficacy of the ESPB to treat pain related to kidney stones in ED patients in comparison to an external control group. The overall study workflow is diagrammed in Figure 1B and Figure 1C. We plan to have our study team members screen for patients based on the availability of the ED ultrasound team - a clinical care team that performs diagnostic and ultrasound guided procedures at the bedside in the ED. Eligible patients will be approached by a study investigator (the proceduralist) who will obtain informed consent and perform the ESPB. The investigator will also collect data from the patient 1 hour after performing the procedure. Follow up assessments using a web-based survey are an optional sub-study. Participants who do not elect to participate in the optional sub-study will receive a telephone call at day 30 to assess only for adverse events. Study participation will be complete after final follow up assessment.

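### Every external control predates the trial, so a calendar shift in second-dose rates could mimic or hide a block effect, and no enrolment-period comparison is planned to show it

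*Combined protocol and SAP*

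**What the plan says.** Section 4.4 of the combined protocol and SAP limits controls to adults with uncomplicated stones, at least one parenteral dose in the ED, and "presentation to the ED between 7/1/2021 and the study start date". Section 2.10 calls them historical: "Up to 180 (3:1 ratio) historical controls will also be included in the study". Section 7.2 makes the 3:1 matched comparison with these controls the primary analysis. The propensity variables there are age, gender, triage acuity, first nursing pain score, comorbidity index and pain medication type. None is a calendar variable, and no sensitivity analysis for time is given. Section 7.4 uses the same controls for ED operations metrics and opioid outcomes.

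On the stability of the rate without ESPB, section 3.6.1 says it "ranges from 47 to 57% for the years 2020 – 2022" and adds: "The average response rate is 53.4% during this period which is in line with historical trends prior to the Covid-19 pandemic". Section 2.10 gives the count behind the average: "572 out of 1071 patients (53.4%) presenting to the ED and meeting the inclusion criteria".

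Two further passages bear on a remedy. Section 5.1 says the team will "screen for patients based on the availability of the ED ultrasound team". Section 6.4 draws participants' and controls' routine data from one EHR query. No reason is given for closing the control window at study start.

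**The concern.** All ESPB patients present after the control window has closed, so period and treatment coincide completely in the primary comparison. Adding a date to the propensity model would not help, because there is no overlap in date to match on. Only a change to the window can separate the two.

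A second parenteral dose, opioid use, length of stay and admission all depend on local practice. Section 3.1 itself mentions recent efforts to cut ED opioid use, which is one way practice could change. The reported 10-point range is half of the planned 20-point effect (55% to 75%, section 2.10). A shift towards fewer second doses would be credited to the block, and a shift towards more would hide a real benefit. As planned, nothing in the results would show which had happened.

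**Working it through.** **Inputs.** 60 ESPB patients and up to 180 controls (2.10). Average response without ESPB 53.4% (2.10, 3.6.1), range 47 to 57% (3.6.1). Planned rates 55% and 75% (2.10). Alpha 0.05 (7.1), with sidedness not stated; I take the control comparison as two-sided. Study length up to 2 years (6.5).

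**1. The plan's own figures.** 572/1071 = 53.4%, as stated. An exact binomial search for Simon's optimal design (0.55 v 0.75, alpha 0.05, beta 0.10) gives 18 then 54 patients: stop at 10 or fewer responses of 18, and reject the null above 35 of 54 (type I error 0.0477, power 0.9007). This matches 18 and 54 in section 2.10. It also matches section 7.3, since 8 or more second doses in 18 means 10 or fewer responses.

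**2. False results under a calendar shift, with no block effect.** Let pT be the response rate in the trial period, pC the rate in the control period, and p = (60 pT + 180 pC)/240. The uncorrected chi-squared test rejects when the observed difference exceeds 1.96 × √[p(1−p)(1/60 + 1/180)].

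Worst case, 57% v 47%:
- p = (34.2 + 84.6)/240 = 0.495
- threshold = 1.96 × 0.0745 = 0.146
- true standard error = √(0.57×0.43/60 + 0.47×0.53/180) = 0.0740
- chance of a result favouring ESPB = 1 − Φ[(0.146 − 0.10)/0.0740] = 1 − Φ(0.62) ≈ 0.27

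Exact enumeration of both binomials gives:

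| Trial period | Control period | False result for ESPB | False result against ESPB |
|---|---|---|---|
| 53.4% | 53.4% | 2.4% | 2.5% |
| 57% | 53.4% | 6.8% | 0.7% |
| 57% | 47% | 26.4% | <0.1% |
| 47% | 53.4% | 0.2% | 13.3% |
| 47% | 57% | <0.1% | 26.9% |

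This ignores correlation from matching and the interim look.

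**3. Is the 47 to 57% range real movement?** I simulated the range under a constant 53.4%, with 1071 patients split into equal or near-equal periods. For three yearly samples (assumed 428/428/215 or 357 each), a 10-point range arises by chance about 2 to 5% of the time. For half-years it is about 25%, and for quarters of about 107 patients about 91%. Section 3.6.1 does not say which period applies.

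**4. Supply of enrolment-period controls.** 1071/30 = 35.7 eligible patients a month, or 35.7 × 24 = 857 over two years. 180 controls plus 60 ESPB patients is 240/857 = 28% of that. The share not approached is undocumented, so these are assumptions:

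| Share not approached | Per month | 12 months | 24 months |
|---|---|---|---|
| one fifth | 7.1 | 86 | 171 |
| one third | 11.9 | 143 | 286 |
| one half | 17.9 | 214 | 428 |

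At one third, 180 is reached after 180/11.9 ≈ 15 months. The 1071 met the inclusion criteria; the exclusions would reduce these counts, and 3:1 matching needs a pool larger than 180.

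**5. Power.** For 75% v 55% with 60 and 180 patients, exact power is 80.7%. With only 60 concurrent controls, p = 0.65, threshold = 1.96 × √(0.65×0.35×2/60) = 0.171 and true standard error = √[(0.1875 + 0.2475)/60] = 0.0851. Power is then Φ[(0.20 − 0.171)/0.0851] = Φ(0.34) ≈ 63%.

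**The case against.** Historical controls are declared openly and are a recognised choice in a single-site phase 2 trial. Section 3.6.1 says the average agrees with pre-pandemic experience, and controls pooled from mid-2021 onwards average over short-term movement. That makes the ends of the range an unlikely pairing. It does not protect one enrolment period against one control window.

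A reader might infer that the untreated rate rose from 47% to 57%, so that drift favours ESPB. Section 3.6.1 gives a range with no order, and drift could as easily work against the block. A reader might also infer that the range is proven instability. That holds only if the periods are years; over quarters, chance alone would usually produce it.

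The strongest objection is to the remedy. Section 5.1 gives no coverage hours, so the existence of many eligible patients who are never approached is an inference. If coverage follows shifts, patients seen without the ultrasound team come at other hours, with possibly different staffing and throughput. Matching on shift would then have little overlap, and matching pre-study controls on calendar quarter would have none. This stands: concurrent controls are not a bias-free replacement. It argues against forcing such matches and for showing the two estimates side by side. It does not argue for leaving the drift unexamined.

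**Conclusion.** The point holds as an inexpensive improvement. Period and treatment are fully confounded in the primary comparison, and the planned propensity model cannot repair this. A shift from the 53.4% average to 57% raises the chance of a false result favouring ESPB from 2.4% to 6.8%. The figures of 26.4% and 26.9% are the worst cases in each direction and should not be read as the expected error rate. All rest on 60 v 180 patients, a two-sided 0.05 test and no block effect.

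Two further inferences are not supported. Simon's rule has its own exposure: its type I error is 8.4% if the true untreated rate is 57%. But it tests against a fixed 55%, so changing the control window would not alter that. Nor do the documents show that concurrent controls are plentiful or comparable; their number and their similarity to ESPB patients are unknown until the query is run.

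**What to change.** - In section 4.4, extend the control window to the end of enrolment, using the EHR query in section 6.4. Apply the trial's eligibility criteria to controls, and exclude anyone approached for the trial or given a block off study.
- In section 7.2, prespecify a matched estimate using only enrolment-period controls, reported beside the estimate using pre-study controls. Use as many controls per ESPB patient as supply allows.
- Compare the untreated response rate before and during enrolment, as a direct check for drift.
- Describe arrival time in both groups and adjust for it only where they overlap. Do not force exact matching on shift or calendar quarter.

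The cost is protocol wording, a wider date range in the consent waiver, and a later query run, so controls cannot be finalised until enrolment closes. No extra ESPB patients are needed. If concurrent controls are few, the concurrent-only estimate will be less precise (about 63% power at 1:1 against about 81% at 3:1). Differences between patients seen with and without the ultrasound team may remain and should be stated as a limitation.

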# 4.5 Minorities, women, and other vulnerable populations or groups

No groups of patients will be specifically excluded except for those with clinical reasons as stated in the exclusion criteria. No patients will be included or excluded based on gender, age, race, or ethnicity.

# 4.6 Screening

- Study team members will screen for patients using the ED track board and other patient lists/reports within MiChart (EPIC EHR)
- Study team members will review potential subjects' presenting symptoms, prior medical history, and imaging findings
- Study team members will then notify a physician investigator on call of potential subjects currently in the ED
- Physician investigator will review inclusion and exclusion criteria with other study team members (if they did not perform screening personally) as well as the potential subject

#### 4.7 Informed Consent

- Written informed consent will be obtained by physician investigators prior to any study procedures are performed
- To limit the possibility of coercion during the consent process, the physician investigator (proceduralist) may not be a member of the primary treatment team in the ED and the primary treatment team will be instructed not to recommend participation in the research study
- A copy of the signed consent document will be provided to the participant, an electronic copy will be uploaded to the study database and a paper original will be stored in a secure location
- For external control patients, a waiver of informed consent will be obtained

# **5 STUDY PROCEDURES**

# 5.1 Study Design and Workflow

This study is designed to be a pragmatic, single treatment arm two-stage trial that investigates the efficacy of the ESPB to treat pain related to kidney stones in ED patients in comparison to an external control group. The overall study workflow is diagrammed in Figure 1B and Figure 1C. We plan to have our study team members screen for patients based on the availability of the ED ultrasound team - a clinical care team that performs diagnostic and ultrasound guided procedures at the bedside in the ED. Eligible patients will be approached by a study investigator (the proceduralist) who will obtain informed consent and perform the ESPB. The investigator will also collect data from the patient 1 hour after performing the procedure. Follow up assessments using a web-based survey are an optional sub-study. Participants who do not elect to participate in the optional sub-study will receive a telephone call at day 30 to assess only for adverse events. Study participation will be complete after final follow up assessment.

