# 7.2 Primary analysis

Our primary analysis will evaluate the proportion of patients receiving ESPB who require a second parenteral pain medication. This outcome will be compared to external control patients who are selected using propensity score matching at a ratio of 3:1. The propensity score model will include the following variables: age, gender, triage acuity level (ESI score), first ED pain score assessed by nursing, Charlson Comorbidity Index, chronic and initial pain medication type. Data for this outcome will be collected via EHR query as above.

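### Screening for ESPB depends on ultrasound-team availability, but control selection and the propensity model ignore time of arrival, so a shift difference in usual care could be read as a block effect

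*Combined protocol and SAP*

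**What the plan says.** On the treated side, section 5.1 plans for study staff to "screen for patients based on the availability of the ED ultrasound team". It continues: "Eligible patients will be approached by a study investigator (the proceduralist) who will obtain informed consent and perform the ESPB". Section 4.6 adds a second dependence on staff: "Study team members will then notify a physician investigator on call of potential subjects currently in the ED". No hours of coverage are given for the ultrasound team or for the on-call investigator.

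On the control side, section 4.4 requires an uncomplicated kidney stone diagnosis, at least one parenteral dose, and "presentation to the ED between 7/1/2021 and the study start date". That date range is the only time condition.

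Section 7.2 matches three controls to each ESPB patient on "age, gender, triage acuity level (ESI score), first ED pain score assessed by nursing, Charlson Comorbidity Index, chronic and initial pain medication type". Arrival hour, shift and weekday are absent. Sections 7.1 to 7.4 contain no other adjustment or sensitivity analysis for timing.

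The primary outcome (section 3.6.1) is the "proportion of patients receiving a second parenteral pain medication in the ED after a single-shot ESPB". Under section 7.4, ED operations metrics are also compared with the external controls; section 3.6.2 lists these as admission, 72-hour return and length of stay.

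**The concern.** Entry to the ESPB group depends on when certain staff are present; entry to the control pool does not. Whether a patient gets a second parenteral dose, how long the patient stays and whether the patient is admitted are decisions or consequences of ED care. They can plausibly vary with staffing and crowding. If they do, the matched comparison mixes the effect of the block with the effect of being treated at the times when the team works.

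This is a different problem from drift between calendar years. Fully concurrent controls drawn from every hour would leave it in place. At stake are the primary contrast and the length-of-stay and admission comparisons. A favourable shift difference could produce a false positive, and an unfavourable one could hide a real benefit.

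**Working it through.** **The plan's own figures.** Section 2.10 reports "572 out of 1071 patients (53.4%) presenting to the ED and meeting the inclusion criteria" without a second dose: 572/1071 = 53.4%, which the plan takes as a 55% baseline against a 75% target. An exact binomial search for Simon's optimal design (55% v 75%, alpha 0.05, beta 0.10) gives 18 patients at stage 1 and 54 in total, as stated. The boundaries are 10/18 and 35/54, with alpha 4.8% and power 90.1%. Stopping at 10 or fewer responders of 18 is the same as section 7.3's rule of 8 or more second doses. No stated figure is in dispute.

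**Bias.** Let f be the share of controls who fall in team hours, and d the usual-care response in team hours minus that in the remaining hours. If ESPB patients reflect team hours and the matching variables absorb none of the difference, then

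bias = (1 − f) × d.

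The documents give neither f nor d. Both are assumptions here.

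**Effect on the test.** Two independent binomials (60 and 180) are enumerated exactly. The control rate is 0.55, the ESPB rate is 0.55 + (1 − f) × d with no block effect, and the test is a two-sided pooled chi-squared at 0.05. Matching is not modelled. With no bias the test rejects 5.0% of the time.

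| f | d = 5 points: bias, rejection | d = 10 points: bias, rejection | d = 15 points: bias, rejection |
|---|---|---|---|
| 1/3 | 3.3 points, 7.2% | 6.7 points, 14.5% | 10.0 points, 27.4% |
| 1/2 | 2.5 points, 6.2% | 5.0 points, 10.2% | 7.5 points, 17.2% |
| 0.75 | 1.25 points, 5.3% | 2.5 points, 6.2% | 3.75 points, 7.8% |
| 0.90 | 0.5 points, 5.0% | 1.0 point, 5.1% | 1.5 points, 5.4% |

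**Opposite sign.** With a true 75% v 55%, exact power is 80.7%. A bias of 5 points against ESPB makes the comparison 70% v 55%, and power falls to 54.5%.

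**Is the control pool large enough to account for timing?** 1071/30 = 35.7 eligible patients a month. The study start date is not stated. An assumed 14.5-month window gives 14.5 × 35.7 ≈ 518 patients. If one third fall in team hours, 518/3 ≈ 173 remain, short of the 180 needed; if one half, about 259. The break-even share is 180/518 ≈ 35%, before exclusions and matching losses. An assumed 18-month window gives about 643, of whom one third is about 214.

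**The case against.** A reader might infer that ESPB patients come only from team hours, that controls come from nights and weekends as well, and that a material bias is therefore established. The documents do not support that.

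- Section 5.1 states a plan to screen by availability and gives no hours. If coverage is continuous, the problem disappears.
- Screening under section 4.6 looks for patients currently in the ED. Someone who arrived before the team came on can still be enrolled, so what depends on the team is the time of screening and block, not strictly the time of arrival. Arrival shift is therefore an imperfect proxy, and the second-dose decision may fall in a later shift.
- There are no data on redosing by hour or weekday. The 47 to 57% range in section 3.6.1 is variation between calendar years. It shows that usual-care response at this site is not constant, but says nothing about shifts.
- Triage acuity, first nursing pain score and initial medication type may absorb part of any shift difference.
- At high coverage the effect on the test is negligible, as the lower rows of the table show.

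All of this stands, and it limits the claim to a possible bias of unknown size. It does not remove the point. Screening according to a team's availability suggests that availability varies, and nothing in the plan shows that the variation is harmless. The listed covariates are fixed early in the visit and cannot be relied on to capture later redosing, staffing or crowding.

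**Conclusion.** The concern holds as an unaddressed source of timing confounding, not as a demonstrated bias. It needs two conditions that the documents leave open: coverage that is less than continuous, and usual care that varies by shift.

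Under an assumed 10-point shift difference with no block effect, two-sided rejection is about 10-15% if one third to one half of controls fall in team hours, and about 5-6% if 75-90% do. The direction is unknown. These figures also assume a 55% control response, no help from the listed covariates, and an ESPB group that fully reflects team hours, so within each assumed pair of values they lean towards the larger effect.

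The case for acting is that the remedy is cheap, rather than that harm has been shown.

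**What to change.** In section 7.2, add arrival shift (day/evening/night) and weekday/weekend to the propensity model, or match exactly on them where numbers allow. Report balance on both after matching. Add a sensitivity analysis limited to controls who presented in the shift and weekday blocks in which ESPB patients were actually enrolled. That definition can be applied to controls who predate the study. A restriction to hours when study screening was running cannot, since no screening took place then, and the documents do not say that past team availability is recorded.

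The cost is a few sentences, with no change to enrolment, sample size or patient contact. Arrival time should be obtainable, because section 6.4 already takes ED operations metrics from the EHR and length of stay is an outcome, although arrival time is not named there. The downside is somewhat fewer close matches. With exact matching, the 3:1 ratio may not be reached if coverage is near one third; in that case, keeping the timing variables in the propensity model is the fallback.
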